8.3.1.7 Overall Survival (OS)

OS is defined as the time from the date of randomisation until death due to any cause. Any patient not known to have died at the time of analysis will be censored based on the last recorded date on which the patient was known to be alive.

Note: Survival calls will be made within 5 days following the date of the data cut-off for each OS analysis, and if patients are confirmed to be alive, or if the death date is post the final data cut-off date, these patients will be censored at the date of the final data cut off. Death dates may be found by checking publicly available death registries.

8.3.1.8 Time to second progression or death (PFS2)

Time from randomisation to second progression or death is defined as the time from the date of randomisation to either the progression event after the start of a subsequent non-study anti-cancer therapy, or death. Determination of PD for second PFS on subsequent anti-cancer therapy will only be collected in those patients who had PD by RECIST 1.1 on study medication (investigator assessed). The date of second progression will be recorded by the investigator and defined according to local standard clinical practice. The date of each scan evaluating tumour response on subsequent therapy and the investigator opinion of progression status (progressed or non-progressed) at each assessment will be recorded in the electronic case report form (eCRF). The site staff should review second progression status and record all subsequent therapy at least every 12 weeks following study medication discontinuation. Patients who are alive and for whom a second disease progression (PFS2) has not been observed should be censored at the last time known to be alive and without a second disease progression, ie, censored at the latest of the PFS or PFS2 assessment date if the patient has not had a second progression or death.

8.3.1.9 HRQoL and symptoms

Patient reported outcomes will be assessed using the FACIT-F and FKSI-19 questionnaires. An outcome variable consisting of a score calculated using respective scoring manuals will be derived for each of the symptom scales/symptom items of these questionnaires. Higher scores on the global health status and functioning scales indicate better health status/function. Higher scores on the symptoms scales indicate greater symptom burden (see Section 5.3.1 for more details). PRO-CTCAE will be analysed descriptively since it is an exploratory endpoint.

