2.2 Secondary objectives

Secondary objective:	Outcome measure:
To compare the efficacy of savolitinib versus sunitinib in patients with MET-driven, unresectable and locally advanced, or metastatic papillary renal cell carcinoma (PRCC)	
 Overall Survival (OS) Objective Response Rate (ORR), duration of response (DoR) and best percentage change in tumour size by BICR using RECIST 1.1 criteria Disease Control Rate (DCR) at 6 and 12 months
To assess the impact of savolitinib and sunitinib on disease related symptoms and health-related QOL in this patient population	
 Mean change from baseline in FKSI-19 and FACIT-F scores
To evaluate the pharmacokinetics of savolitinib in this patient population	
 PK concentration data

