5.3.1.1 Functional Assessment of Chronic Illness Therapy – Fatigue

The validated Functional Assessment of Chronic Illness Therapy-Fatigue (FACIT-F) (now in Version 4) is a 40-item instrument. It comprises the 4 domains from the FACT-G (Physical Well-Being, Social/Family Well-Being, Emotional Well-Being, and Functional Well-Being) as well as a 13-item 'additional concerns' domain that captures information about fatigue. (Appendix I).

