5.3.1.2 Functional Assessment of Cancer Therapy Kidney Symptom Index-19

The Functional Assessment of Cancer Therapy Kidney Symptom Index-19 (FKSI-19) is a validated instrument designed to accurately assess patient self-reported symptom burden to determine treatment impact and evaluate clinical benefit in patients with renal cancer (Rao et al 2009). The instrument includes 19 items covering 4 subscales: Disease-Related Symptoms Subscale – Physical, Disease-Related Symptoms Subscale – Emotional, Treatment Side Effects Subscale, Function and Well-Being Subscale; responses are reported as it applies to the past 7 days (Appendix J).

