8.4.2 Analysis of the secondary variable(s)

Objective Response and Disease Control Rates

ORR and DCR will be presented with a two-sided 95% CIs using Clopper-Pearson method (Clopper and Pearson, 1934). The number and percentage of patients in each response category (CR, PR, SD, PD, NE) will be summarised. Results may be summarised by the IMDC risk category if patient numbers permit.

Duration of response

Kaplan-Meier plots of duration of response in the responding patients will be produced.

Change in tumour size

The best change in target lesion tumour size from baseline (where best change in target lesions size is the maximum reduction from baseline or the minimum increase from baseline in the absence of a reduction) will also be summarised.

Waterfall plots (bar charts) indicating the best percentage change from baseline in sum of the diameters of TLs will be produced. Reference lines at the +20% and 30% change in tumour size levels will be added to the plots, which correspond with the definitions of progression and ‘complete or partial’ response respectively.

Overall Survival

Summaries (number of deaths, medians, and proportion alive at 1 year) and Kaplan Meier plots will be provided.

Time to second progression or death (PFS2)

Summaries (number of 2nd progression events or deaths, medians, and proportion alive at 1 year) and Kaplan Meier plots will be provided.

PRO analyses

Analyses on the FACIT-F, FKSI-19, EQ-5D-5L and PRO-CTCAE will be based on the instruments’ scoring manuals.

Descriptive statistics will be calculated for each scheduled visit/time point in the study, for each trial arm and as a total. These will report the number of patients, the number of EQ-5D questionnaires completed at each visit, the number and proportion responding to each dimension of the EQ-5D-5L. Additionally, summary statistics (eg, n, mean, median, sd, min, max) will be reported for the EQ-5D index score and the EQ-VAS score, and the change from baseline for the EQ-5D index score and the EQ-VAS score.

To support submissions to payers, additional analyses may be undertaken and these will be outlined in a separate Payer Analysis Plan.

Safety analyses

Safety data will not be analysed formally. Standard data summaries will be produced for safety data including (but not limited to):

- Summaries of AEs of any CTCAE grade – summarised by MedDRA preferred term and system organ class and CTCAE grade.
- Summaries of Grade 3 and above AEs.
- SAEs.

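### Does the score-direction rule in Section 8.3.1.9, which does not fit the FACIT-F and FKSI-19 scales, put the patient-reported endpoint at risk?

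*Protocol*

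**What the plan says.** The secondary endpoint in Protocol Section 2.2 is "Mean change from baseline in FKSI-19 and FACIT-F scores". Section 8.3.1.9 names FACIT-F and FKSI-19 as the instruments and says that a score calculated from the respective scoring manuals "will be derived for each of the symptom scales/symptom items of these questionnaires". It then gives two directions: "Higher scores on the global health status and functioning scales indicate better health status/function", and "Higher scores on the symptoms scales indicate greater symptom burden". For more detail it refers to Section 5.3.1.

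Section 5.3.1.1 describes FACIT-F as a 40-item instrument: "It comprises the 4 domains from the FACT-G (Physical Well-Being, Social/Family Well-Being, Emotional Well-Being, and Functional Well-Being"), plus a 13-item domain that "captures information about fatigue. (Appendix I"). Section 5.3.1.2 gives FKSI-19 four subscales: two for disease-related symptoms (physical and emotional), followed by "Treatment Side Effects Subscale, Function and Well-Being Subscale".

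Section 8.4.2 returns to scoring: "Analyses on the FACIT-F, FKSI-19, EQ-5D-5L and PRO-CTCAE will be based on the" instruments' scoring manuals. Section 8.1 makes all secondary analyses descriptive and announces a separate statistical analysis plan, which was not available for this review.

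**The concern.** The direction rule reads as though written for a different questionnaire.

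- It gives a direction to a global health status scale, which neither instrument has.
- Several FACIT-F and FKSI-19 scales are neither functioning nor symptom scales by name, so the rule does not reach them.
- The derivation sentence speaks only of symptom scales and items, while the endpoint covers both instruments' scores.
- The pointer to Section 5.3.1 does not help. That section gives no direction for either instrument, and its FACIT-F paragraph sends the reader to Appendix I, the list of QT-prolonging drugs. The questionnaires are in Appendix J.

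With no test on this endpoint, a reader takes the result from the sign of the mean change. If the protocol's sentence said higher is worse while the manual keyed the same scale as higher is better, an improvement could be written up as a greater symptom burden.

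**Working it through.** **Inputs.** Scale names come from Sections 5.3.1.1 and 5.3.1.2. Item counts and wording come from the Appendix J forms, where each item is coded 0 to 4. The row labels of the FKSI-19 form are displaced in the text as read, so its items are assigned to subscales by content.

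**Step 1: reproduce the stated sizes.** FACIT-F: 7 + 7 + 6 + 7 + 13 = 40. FKSI-19: 12 + 1 + 3 + 3 = 19. Both agree with the protocol. Scales: 5 + 4 = 9.

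**Step 2: match each scale name to the rule.**

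| Scale | Items | Positively / negatively worded | Class by name |
|---|---|---|---|
| FACIT-F Physical | 7 | 0 / 7 | none |
| FACIT-F Social/Family | 7 | 7 / 0 | none |
| FACIT-F Emotional | 6 | 1 / 5 | none |
| FACIT-F Functional | 7 | 7 / 0 | functioning |
| FACIT-F fatigue | 13 | 2 / 11 | none (possibly symptom) |
| FKSI-19 disease symptoms, physical | 12 | 2 / 10 | symptom |
| FKSI-19 disease symptoms, emotional | 1 | 0 / 1 | symptom |
| FKSI-19 side effects | 3 | 0 / 3 | none (possibly symptom) |
| FKSI-19 function and well-being | 3 | 3 / 0 | functioning |

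Global health status matches 0 of 9, functioning 2 and symptoms 2. That leaves 9 − 4 = 5 with no direction.

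**Step 3: test how firm the five is.**

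- Strict reading: 5 scales, holding 7 + 7 + 6 + 13 + 3 = 36 of 59 items (61%).
- Fatigue counted as a symptom scale: 4 scales, 36 − 13 = 23 of 59 items (39%).
- Fatigue and side effects both counted: 3 scales, 23 − 3 = 20 of 59 items (34%).

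The FACIT-F physical, social/family and emotional domains stay uncovered on all three readings.

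**Step 4: ask whether a score could be computed from these sentences.** Take a scale with *p* positively and *n* negatively worded items. Its unreversed sum is 4*p* at best health and 4*n* at worst. For the fatigue domain that is 4 × 2 = 8 at best and 4 × 11 = 44 at worst, on a possible range of 0 to 52. An unreversed sum is therefore not a usable score. Items must be reversed first, and the protocol gives the reversal only by reference to the manuals. Whoever computes the score must have the manual open, and the reversal it prescribes sets the direction.

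**Step 5: see what a wrong direction could alter.** Assume simple sums with complete items. With *k* = *p* + *n*, the two possible keyings satisfy S(higher = better) = 4*k* − S(higher = worse), so a change on one is minus the change on the other. The size of each arm's mean change is the same either way. Only the verbal reading of the sign could differ.

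**Step 6: bound the misreading.** The manuals are not in the protocol, so both keyings are assumptions. If symptom scales are keyed higher = worse, the rule agrees with them and 0 of 19 FKSI-19 items are misdescribed. If higher = better, 12 + 1 = 13 of 19 are. Treating fatigue as a symptom scale adds either 0 or 13 of 40 FACIT-F items.

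**The case for a change.** The best case for amending the text is that the fault lies in what the protocol states, not in what it leaves out. Section 8.3.1.9 could simply have deferred to the manuals. Instead it also asserts directions, one of them for a scale that does not exist. The version history records that this section was revised in Version 6.0 for how these scores are calculated, so the mismatch sits in recently handled text. The repair would be cheap: a few sentences and one letter.

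Part of this stands. The global health status label fits nothing, three domains have no direction on any of the readings above, and the Appendix I reference is wrong. The rest does not carry far:

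- A conflict between the rule and the manuals is possible but not shown; it depends on sources outside the protocol.
- The objection that opposite directions cannot both apply to a total score needs a total score, and Section 8.3.1.9 mentions none.
- Which totals or subscales to tabulate, and the direction of each, is ordinary content for a statistical analysis plan.
- A rewritten sentence that avoided guessing would have to say that direction is as the manual sets it, which adds little to the delegation already in Sections 8.3.1.9 and 8.4.2.
- The appendix slip misleads no one for long. Sections 5.3.1.2 to 5.3.1.4 cite Appendix J correctly, and the version history shows the QT appendix was added in Version 4.0, so a missed renumbering is the likely cause.

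**Conclusion.** No change to the plan follows. The observation is accurate: one named scale exists in neither instrument, and three to five of nine scales receive no direction, depending on how strictly names are matched. But the scores are computed from the scoring manuals, so no score, no size of mean change and no comparison between arms depends on the two sentences. The endpoint is secondary and descriptive in about 50 patients, and no power, error rate or primary result is touched.

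The only exposure is a misworded reading of a sign, ranging from 0 to 13 of 19 FKSI-19 items, and from 0 to 13 of 40 FACIT-F items if fatigue counts as a symptom scale. The document does not show that the true figure is above zero. What is left is two clerical slips (a stray label and a wrong appendix letter) and a gap that analysts fill when they apply the manuals.

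This rests on two assumptions: that the manuals are followed as Sections 8.3.1.9 and 8.4.2 require, and that the tables and text take the direction of improvement from the same source as the scores. The content-based assignment of FKSI-19 items affects the item counts but not the nine-scale count.

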8.4 Methods for statistical analyses

All efficacy analyses will be performed on the FAS populations. Results of all statistical analyses will be presented using a 95% confidence interval and 2-sided p-value.

The below mentioned general principles will be followed throughout the study:

- Descriptive statistics will be used for all variables, as appropriate. Continuous variables will be summarised by the number of observations, mean, standard deviation, median, minimum, and maximum. Categorical variables will be summarised by frequency counts and percentages for each category.
- Unless otherwise stated, percentages will be calculated out of the population total and for each treatment group.

Baseline will be the last assessment of the variable under consideration prior to the intake of the first dose of investigational product, except for efficacy variables. For efficacy variables, baseline is defined as the last visit prior to randomisation.

Efficacy and HRQoL data will be summarised based upon the FAS analysis set. Safety and treatment exposure data will be summarised based upon the safety analysis set by actual treatment received. Study population and demography data will be summarised based upon the FAS analysis set.

8.4.1 Analysis of the primary variable (s)

The log-rank test will be stratified by IMDC risk group (poor, intermediate, favourable) and line of therapy (1st line; previously treated with an anti-VEGF TKI; previously treated without an anti-VEGF TKI) providing there are at least 10 PFS events within each strata. If not, then the log-rank test will be stratified by IMDC risk group only, providing there are at least 10 PFS events within each strata. If not, then the log-rank test will be unstratified.

The effect of treatment will be estimated by the HR together with its corresponding 95% CI and p-value. Kaplan Meier plots will be provided.

8.4.2 Analysis of the secondary variable(s)

Objective Response and Disease Control Rates

ORR and DCR will be presented with a two-sided 95% CIs using Clopper-Pearson method (Clopper and Pearson, 1934). The number and percentage of patients in each response category (CR, PR, SD, PD, NE) will be summarised. Results may be summarised by the IMDC risk category if patient numbers permit.

Duration of response

Kaplan-Meier plots of duration of response in the responding patients will be produced.

Change in tumour size

The best change in target lesion tumour size from baseline (where best change in target lesions size is the maximum reduction from baseline or the minimum increase from baseline in the absence of a reduction) will also be summarised.

Waterfall plots (bar charts) indicating the best percentage change from baseline in sum of the diameters of TLs will be produced. Reference lines at the +20% and 30% change in tumour size levels will be added to the plots, which correspond with the definitions of progression and ‘complete or partial’ response respectively.

Overall Survival

Summaries (number of deaths, medians, and proportion alive at 1 year) and Kaplan Meier plots will be provided.

Time to second progression or death (PFS2)

Summaries (number of 2nd progression events or deaths, medians, and proportion alive at 1 year) and Kaplan Meier plots will be provided.

PRO analyses

Analyses on the FACIT-F, FKSI-19, EQ-5D-5L and PRO-CTCAE will be based on the instruments’ scoring manuals.

Descriptive statistics will be calculated for each scheduled visit/time point in the study, for each trial arm and as a total. These will report the number of patients, the number of EQ-5D questionnaires completed at each visit, the number and proportion responding to each dimension of the EQ-5D-5L. Additionally, summary statistics (eg, n, mean, median, sd, min, max) will be reported for the EQ-5D index score and the EQ-VAS score, and the change from baseline for the EQ-5D index score and the EQ-VAS score.

To support submissions to payers, additional analyses may be undertaken and these will be outlined in a separate Payer Analysis Plan.

Safety analyses

Safety data will not be analysed formally. Standard data summaries will be produced for safety data including (but not limited to):

- Summaries of AEs of any CTCAE grade – summarised by MedDRA preferred term and system organ class and CTCAE grade.
- Summaries of Grade 3 and above AEs.
- SAEs.

- Any AE occurring within the defined 30 day follow up period after discontinuation of investigational product will be included in the AE summaries.
- Deaths will be summarised by primary cause, along with AEs with an outcome of “fatal”.
- Haematology, clinical chemistry, vital signs, ECG, ECHO/MUGA data and concomitant medication will be summarised.
- Any qualitative safety assessments for urinalysis will be presented as is deemed appropriate. This may include, but is not restricted to, presentation of parameters against time, concentration, or shift plots. Appropriate scatter plots will also be considered to investigate trends in parameters compared with baseline.

8.4.3 Subgroup analysis

No subgroup analysis will be performed.

8.4.4 Interim analysis

An interim futility analysis of PFS was planned to be conducted when a total of approximately 36 PFS events confirmed by BICR had been observed (30% of 121 PFS events, which was estimated to occur 17 months after the first patient had been randomised). Following IDMC endorsement to terminate recruitment into SAVOIR, the interim analysis will not occur.

8.4.5 Sensitivity analysis

Investigator assessment:

PFS will be reported per investigator assessment.

8.4.6 Exploratory analyses

8.4.6.1 Pharmacokinetics

The savolitinib plasma concentration data obtained from the samples collected in this study may be included in the listings of the CSR but these data will be pooled with data from other studies in order to perform a population PK analysis. The results of this analysis will be reported in a separate population PK report.

8.4.6.2 Pharmacogenetic research and statistical methods, and determination of sample size

The number of patients that will agree to participate in the genetic research is unknown. It is therefore not possible to establish whether sufficient data will be collected to allow a formal statistical evaluation or whether only descriptive statistics will be generated. A statistical analysis plan will be prepared where appropriate.

9. STUDY AND DATA MANAGEMENT BY ASTRAZENECA

9.1 Training of study site staff

Before the first patient is entered into the study, an AstraZeneca representative will review and discuss the requirements of the Clinical Study Protocol and related documents with the investigational staff and also train them in any study specific procedures and the WBDC and ePRO systems utilised.

The Principal Investigator will ensure that appropriate training relevant to the study is given to all of these staff, and that any new information relevant to the performance of this study is forwarded to the staff involved.

The Principal Investigator will maintain a record of all individuals involved in the study (medical, nursing and other staff).

9.2 Monitoring of the study

During the study, an AstraZeneca representative will have regular contacts with the study site, including visits to:

- Provide information and support to the investigator(s).
- Confirm that facilities remain acceptable.
- Confirm that the investigational team is adhering to the Clinical Study Protocol, that data are being accurately and timely recorded in the eCRFs, that biological samples are handled in accordance with the Laboratory Manual and that study medication accountability checks are being performed.
- Perform source data verification (a comparison of the data in the eCRFs with the patient's medical records at the hospital or practice, and other records relevant to the study) including verification of informed consent of participating patients. This will require direct access to all original records for each patient (eg, clinic charts).
- Ensure withdrawal of informed consent to the use of the patient's biological samples is reported and biological samples are identified and disposed of/destroyed accordingly, and the action is documented, and reported to the patient.

The AstraZeneca representative will be available between visits if the investigator(s) or other staff at the centre needs information and advice about the study conduct.

9.2.1 Source data

Refer to the Clinical Study Agreement (CSA) for location of source data.

9.2.2 Study agreements

The Principal Investigator at each centre should comply with all the terms, conditions, and obligations of the Clinical Study Agreement (CSA), or equivalent, for this study. In the event of any inconsistency between this Clinical Study Protocol and the CSA, the terms of Clinical Study Protocol shall prevail with respect to the conduct of the study and the treatment of patients and in all other respects, not relating to study conduct or treatment of patients, the terms of the Clinical Study Agreement shall prevail.

Agreements between AstraZeneca and the Principal Investigator should be in place before any study-related procedures can take place, or patients are enrolled.

